#### **Baseline Assessment (20-29 weeks gestation):**

A trained research worker will administer the Hamilton Anxiety Scale (HAM-A) and Hamilton Depression Scale (HAM-D) to the participant.

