#### **Prenatal Session 1 (28-32 weeks gestation)**

At this time point, if the individual agrees to participate in this session and gives consent, the individual is randomly assigned to one of two groups: Intervention vs. Enhanced Treatment As Usual (ETAU). When the participants are 28-32 weeks pregnant, they participate in an in-person session (pre-COVID) or in a virtual session (during COVID), either by phone or video call, and are asked to complete mood assessments, a cognitive assessments and answer questionnaires about feelings, life events, and sleep. Participants are asked a questionnaire about the effect of COVID-19 on their lives. In total, these questionnaires take about 90 minutes. All questionnaire results are entered in Redcap, an online secure database. All information entered in REDCap is de-identified using a screen ID. At home, we ask participants to wear an activity monitor for 7 full 24-hour days. We ask participants to complete a sleep diary noting sleep times and durations for the seven consecutive days they are wearing the activity monitor.

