### List of Instruments and Standardized Protocols:

Data Collection Instrument	Screening (20-29 weeks)	Prenatal 1 (28-32 weeks)	Prenatal 2 (34-39 weeks)	Newborn	6 week	12 week	16 week
Demographics		X	X		X	X	X
Newborn Delivery Data				X			
Pregnancy Medical History	X						

Predictive Index of Postnatal Depression (PIPD)	X						
Mini International Neuropsychiatric Interview (MINI)	X						
Columbia Suicide Severity Rating Scale (C-SSRS)	X	X	X		X	X	X
Edinburgh Postnatal Depression Scale (EPDS)	X	X	X		X	X	X
Hamilton Anxiety Scale (HRSA)	X	X	X		X	X	X
Hamilton Depression Scale (HRSD)	X	X	X		X	X	X
Personal Health Questionnaire-9 (PHQ-9)		X	X		X	X	X
Pittsburgh Sleep Quality Index (PSQI)		X	X		X	X	X
Pregnancy Physical Activity Questionnaire (PPAQ)		X	X				
Family History Screen (FHS)				X			
Adverse Childhood Experiences Questionnaire (ACE)		X					
Benevolent Childhood Experiences scale (BCEs)		X					
The Hunger Vital Sign (HVS)		X	X		X		X
Experiences in Close Relationships (ECR)		X					
Childhood Trauma Questionnaire (CTQ)		X					
Multidimensional Scale of Perceived Social Support Questionnaire (MSPSS)		X			X		
Maternal Antenatal Attachment Scale (MAAS)			X				
Abbreviated Brief Infant Sleep Questionnaire (BISQ)					X		X
Childcare Arrangement Scale (CAS)					X		X
Infant Intentionality Questionnaire (IIQ)					X		X
Infant Nutrition Questionnaire (INQ)					X		X
Karitane Parenting Confidence Scale (KPCS)					X		X
Short Acculturation Scale for Hispanics (SASH)			X				
Experiences of Discrimination (EOD)			X				

Adult Attachment Questionnaire (AAQ)		X	X				
Maternal Postnatal Attachment Scale (MPAS)					X		X
Being a Mother (BaM-13)							X
Parental Bonding Instrument for Mothers (PBI-M)		X	X				
Parental Bonding Instrument for Fathers (PBI-F)		X	X				
Rejection Sensitivity Questionnaire (RSQ)		X					
Difficulties in Emotion Regulation Scale (DERS)		X	X		X		
Interpersonal Support Evaluation List (ISEL)		X					
COVID-19 Questionnaire		X					X
Utilization of PREPP Skills		X	X		X		X
Infant EEG				X	X		
Adult Activity Monitor		X	X		X		X
Sleep Log		X	X		X		X
Infant Smart Sleep Sensor					X		X
Baby Day Diary					X		X
Infant Care Routine, video					X		X
Modified 'double' Still Face Protocol, video (SFP)							X
Free Play, Video							X

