#### **Statistical Analysis Plan**

**Overall.** Based on preliminary data, we anticipate minimal attrition ( $\leq 5\%$ ) during the first two assessment sessions (pre-delivery), and up to 33% attrition postpartum across both groups in the worst-case scenario. All participants with data available for a given study phase (pre- or postpartum) will be included in the primary analyses. Before conducting hypothesis tests, we will screen all variables at all time points for out-of-range values, outliers, and data inconsistencies. Means, standard deviations, interquartile range, minima, and maxima for continuous variables and proportions for categorical variables will be reported.

Following CONSORT guidelines, the primary analyses for all aims will follow an intention-to-treat (ITT) approach, including all randomized participants regardless of treatment adherence or dropout. If significant imbalances in baseline covariates (e.g., maternal age, BMI, birth order, infant sex) are observed despite randomization, these variables will be included as covariates in the models. Additional exploratory models will examine relevant biological factors, such as maternal BMI, fetal/infant sex, maternal age, infant gestational age at birth, and birthweight corrected for birth age, as potential covariates.

**Aim 1.** Reduce women's distress during pregnancy. We hypothesize that PREPP will be associated with: (A) Diminished depressive symptoms using interviewer-rated and self-report questionnaires; (B) Improved perception of sleep quality relative to objective changes in sleep duration (per self report and actigraphy).

**Analysis for Aim 1A:** For depressive symptom outcomes (HRSD, PHQ-9, HRSA, PSQI, EPDS), we will fit linear mixed-effects models with fixed effects for Treatment (PREPP vs. ETau), Time (2nd and 3rd assessments), and birth order, along with subject-specific random intercepts. For EPDS, we will adjust for the screening score and test a Treatment  $\times$  Screening Score interaction as a secondary analysis. Additional moderators will also be tested.

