**Analysis for Aim 1B:** Two ActiGraph-derived measures, total sleep time (TSTact) and sleep efficiency (SEact), will serve as outcomes in separate mixed-effects models with fixed effects for time and day (within the ActiGraph epoch) and subject-specific random intercepts, assuming an AR(1) correlation structure. We will assess whether adjustment for weekday/weekend is warranted. Subject-specific means of these measures will be used as predictors of their subjective

counterparts (TSTact, SEact) in additional mixed models testing for treatment group differences in the association between objective and subjective sleep measures. Moderation by trauma history and attachment will be explored.

**Aim 2. Determine the maintenance of improved maternal mood and differences in infant behavior.** We hypothesize that PREPP will be associated with: (A) Lower rates of PPD and distress, including poor sleep efficiency, assessed by interviewer-rated and self-report questionnaires as well as sleep actigraphy. (B) Less infant fuss/cry behavior and longer nocturnal sleep bouts based on maternal report and actigraphy.

**Analysis for Aim 2A:** Separate linear mixed-effects models will be used for each maternal mood outcome (PHQ-9, HRSD, EPDS, HRSA, PSQI) and ActiGraph-derived sleep measures. Models will include Treatment, Time (6, 12, and 16 weeks postpartum), and their interaction, with baseline (pregnancy) values as covariates. Subject-specific random intercepts will be included. The primary parameter of interest is the Treatment  $\times$  Time interaction; if non-significant, the main effect of Treatment will be tested. PPD diagnosis will be modeled using mixed-effects logistic regression with analogous fixed effects.

For infant outcomes (6 and 16 weeks), linear mixed-effects models will assess Treatment effects without Time  $\times$  Treatment interaction. Sleep data will be processed as in Aim 1B. Covariates include time-varying factors such as weaning, solid food introduction, maternal return to work, and social support. Moderators (infant sex, trauma history, attachment) will also be assessed.

**Analysis for Aim 2B:** Infant sleep and cry behavior at 6 and 16 weeks will be compared using mixed-effects models with Treatment, Time, and their interaction as fixed effects. Covariates and secondary analyses will be same as those in Aim 2A.

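### Aim 1A adjusts only EPDS for its pre-randomisation score, although HRSD and HRSA are also scheduled before randomisation; adjusting them too would gain precision at no cost.

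*Combined protocol and SAP*

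**What the plan says.** Under Analysis for Aim 1A, the Statistical Analysis Plan sets one common model for five scales: "For depressive symptom outcomes (HRSD, PHQ-9, HRSA, PSQI, EPDS), we will fit linear mixed-effects models with fixed effects for Treatment". The remaining terms are "Time (2nd and 3rd assessments), and birth order, along with subject-specific random intercepts". A pre-randomisation score then enters for one scale only: "For EPDS, we will adjust for the screening score". A treatment-by-screening-score interaction for EPDS is planned as a secondary analysis.

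The Hamilton scales are scheduled at the same stage. The Baseline Assessment section (20-29 weeks) states: "A trained research worker will administer the Hamilton Anxiety Scale (HAM-A) and Hamilton Depression Scale (HAM-D) to the participant". The instrument table, which abbreviates these scales as HRSA and HRSD, marks both at Screening and again at both prenatal sessions. PHQ-9 and PSQI have no Screening mark. Random assignment takes place at Prenatal Session 1 (28-32 weeks).

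Two other provisions bear on the point. The overall section of the plan has a conditional covariate rule: "If significant imbalances in baseline covariates (e.g., maternal age, BMI, birth order, infant sex) are observed despite randomization", those variables are added to the models. Aim 2A fits the maternal mood outcomes "with baseline (pregnancy) values as covariates".

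**The concern.** A scale's own earlier value is usually among the best predictors of its later value. Adjusting for it in a randomised comparison removes variance from the treatment estimate without changing what is estimated. Aim 1A does this for EPDS but not for HRSD or HRSA, although both are due to be measured before allocation. Aim 2A does adjust its mood outcomes for a pregnancy value.

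Two other parts of the plan might seem to do the same job, but neither does:

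- **The random intercept.** Only the second and third assessments are outcomes. If screening is the first, the 20-29 week score is neither an outcome nor a covariate, so the intercept cannot draw on it.
- **The imbalance rule.** It acts only after a significant imbalance is seen. The precision gained from a prognostic covariate does not depend on imbalance.

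At stake are the interviewer-rated tests of hypothesis 1A, which would have wider confidence intervals than the scheduled data allow.

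**Working it through.** **Inputs from the Power analysis paragraph.** N = 214, so 107 per arm; 5% attrition for Aim 1; alpha 0.01 after Bonferroni for five outcomes; within-subject correlation r = 0.2; stated detectable effect d = 0.48.

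**Assumptions.** The test is two-sided. Power is 80%, which the plan states for Aim 2 but not for Aim 1. All correlations among baseline and the two follow-up visits are equal. The treatment effect is the same at both visits. The second and third assessments are Prenatal 1 and Prenatal 2.

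**Step 1: reproduce the stated figure.** Women per arm: 107 × 0.95 = 101.65. For an unadjusted comparison at one visit,

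d = (2.576 + 0.842) × √(2/101.65) = 0.479.

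Power at d = 0.48 is 80.1%. The plan's figure therefore matches a single-visit comparison that takes no credit for a second visit or for baseline adjustment.

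**Step 2: mean of two visits, without and with baseline.** In units of the single-visit variance, the mean of two visits has variance (1 + r)/2. Adjusting for a baseline score with correlation r to each visit subtracts r², which leaves (1 + r)/2 − r². The detectable d is 0.479 times the square root of the variance.

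| Correlation | Variance, unadjusted | Variance, adjusted | Reduction | Detectable d |
|---|---|---|---|---|
| 0.2 (the plan's r) | 0.60 | 0.56 | 0.04/0.60 = 6.7% | 0.371 → 0.359 |
| 0.5 (assumed) | 0.75 | 0.50 | 0.25/0.75 = 33% | 0.415 → 0.339 |
| 0.7 (assumed) | 0.85 | 0.36 | 0.49/0.85 = 58% | 0.442 → 0.288 |

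A simulation of 3,000 trials with 102 women per arm gave variance reductions of 6.8%, 32.7% and 56.6%, in line with the formula.

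**Step 3: one visit only.** The variance is multiplied by 1 − r².

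| Baseline correlation | Detectable d (unadjusted 0.479) | Power at d = 0.48 (unadjusted 80.1%) |
|---|---|---|
| 0.2 (the plan's r) | 0.470 | 82.0% |
| 0.4 (assumed) | 0.439 | 87.7% |
| 0.5 (assumed) | 0.415 | 91.6% |

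The documents give no baseline-to-follow-up correlation for either Hamilton scale. Using r = 0.2 for that purpose is itself an assumption, and the higher values only show how the gain grows.

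**The case against.** The strongest reply is that little is lost. At the only correlation the plan states, the detectable d moves by 0.012, and the stated d = 0.48 is reached without any adjustment. That stands: the larger gains rest on correlations the documents do not give.

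Some stronger inferences are tempting, but the documents do not support them:

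- **That EPDS was singled out for no reason.** EPDS is an eligibility instrument (a score of 7 or more is one route in), and its screening score also serves a planned interaction test. The Hamilton scales have neither role. This explains why EPDS is adjusted; it does not argue against adjusting the other two.
- **That a chance baseline difference passes in full into the estimated effect.** Only the correlated fraction does, about one fifth at r = 0.2. The imbalance rule could also admit a Hamilton score, since its list is only of examples. That safeguard is weaker than prespecification because it is conditional.
- **That a baseline Hamilton score exists for every woman.** It is scheduled, but it is not an eligibility criterion and its completeness is not stated. A covariate with missing values and no handling rule would drop randomised women, contrary to the intention-to-treat statement.
- **That Aim 2A shows the 20-29 week score to be the plan's general baseline.** It cannot be for PHQ-9 and PSQI, which have no screening value. Aim 2A shows only that the plan accepts baseline adjustment in principle.

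The two-visit figures also need a constant effect at Prenatal 1 and Prenatal 2. Randomisation, the Prenatal 1 questionnaires and the first intervention session all fall at 28-32 weeks, and their order is not given. If the Prenatal 1 scores precede treatment, a detectable d for the two-visit mean has little meaning, and the one-visit figures are the better guide.

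**Conclusion.** The point holds as a matter of efficiency. For HRSD and HRSA, Aim 1A leaves out a prognostic score that is scheduled before randomisation, while the plan makes that adjustment for EPDS. The gain from adjusting is modest at r = 0.2 and about a one-third cut in variance if the correlation is 0.5. These figures rest on the assumptions listed with the calculation, above all on a correlation that the documents do not report for these scales.

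A reader might infer that the Aim 1 comparison is biased or underpowered. Neither follows. The randomised comparison is valid without the covariate, type I error is unaffected, and d = 0.48 reproduces without adjustment. A reader might also take HRSD and HRSA as named primary outcomes. The Power analysis counts five primary outcomes across Aims 1 and 2 without naming them. The five scales listed in both Aim 1A and Aim 2A match that count, so it is a reasonable inference and no more. Aim 2A also analyses actigraphy measures and PPD diagnosis.

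**What to change.** In Analysis for Aim 1A, prespecify the 20-29 week HRSD score as a covariate in the HRSD model and the 20-29 week HRSA score in the HRSA model, unconditionally, as for EPDS. Add a simple rule for any missing baseline score, such as mean imputation or a missing indicator, so that all randomised women remain in the analysis.

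In the same edit, say which sessions are the second and third assessments, since the overall section separately calls the pre-delivery sessions the first two. Also say whether the Prenatal 1 scores are taken before or after randomisation and the first intervention session.

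PHQ-9 and PSQI have no screening value. Using the screening EPDS score in those models is optional: no figure in the documents shows what it would gain, least of all for a sleep-quality scale.

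The cost is a few sentences in the plan, with no new data, visits or participants. This is a free improvement.

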## **6-Week Postpartum Session**

At 6 weeks postpartum, participants are asked to participate in another session (in-person if pre-COVID or virtual if during COVID), to complete mood assessments. This session is about an hour. During this session, participants are videotaped as they engage in a standard routine of infant care. This takes about 5 minutes to complete.

If the session is completed in-person (not virtually), participants are invited to complete the infant EEG. We will examine variation in EEG left/right power asymmetry in relation to potential group differences in the effectiveness of the intervention in helping mothers function as a social "buffer" and modulate infant reactivity. The 6-week postpartum EEG sleep protocol takes place while the baby is sleeping. This is a non-clinical EEG recording. A cap with EEG sensors is placed on the newborn's head by a trained member of the research team. The research team then waits for the baby to enter a state of quiet sleep. This allows the research team time to measure brain activity while the baby sleeps. The participant is reassured by the research team that although the sensors might leave a red mark briefly after they are removed, this procedure is completely painless and does not harm the newborn.

The EEG session takes approximately 30 minutes. This session is video recorded to allow the researchers to collect information about infant behavior during the session. In total, including setup of materials and video-recording, the 6-week EEG session is approximately 1.5 hours in duration.

The participant is allowed extra time to pick up, feed, comfort, or change the infant to accommodate fussiness or discomfort at any time during the EEG. If the participant is uncomfortable with the EEG, they are free to stop the session.

Participants wear an activity monitor again for 7 full days. While wearing the monitors, participants complete a sleep diary noting sleep times and durations, which takes about 5-10 minutes. Participants in the treatment group are asked to complete a diary entry that asks them the frequency and duration of their utilization of the skills learned from PREPP (i.e., carrying/holding baby, accentuation of day/night cues, focal feeding, use of swaddling,

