mindfulness techniques). These questions take about 10 minutes to complete. Infant sleep is assessed using a Smart Sleep Sensor worn by the infant. The Sensor detects day and night sleep activity by recording activity patterns during the time intervals in which it is worn. Infants wear the Sensor for four days (24- hour periods).

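### The daily actigraphy model has no session-level variance term, so standard errors for between-session contrasts may be too small; Aim 2 does not say whether it uses daily values

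*Combined protocol and SAP*

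**What the plan says.** All analysis references are to the Statistical Analysis Plan.

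- **Aim 1B.** The two actigraphy outcomes, total sleep time and sleep efficiency, have "fixed effects for time and day (within the ActiGraph epoch) and subject-specific random intercepts, assuming an AR(1) correlation structure". The day effect and the planned weekday/weekend check show that the unit is the day. No subject-by-session effect, robust standard error or session-level averaging is stated for these outcome models. Subject means appear only as predictors of self-reported sleep. The sentence does not say whether AR(1) restarts at each session, and it lists no Treatment term.
- **Aim 2A, mothers.** "Separate linear mixed-effects models will be used for each maternal mood outcome (PHQ-9, HRSD, EPDS, HRSA, PSQI) and ActiGraph-derived sleep measures". Treatment x Time is the main target; "if non-significant, the main effect of Treatment will be tested". On random effects: "Subject-specific random intercepts will be included". AR(1) and day are not mentioned, nor is the choice between daily values and session means.
- **Aim 2A, infants.** These models leave out the Treatment x Time interaction, and the paragraph adds: "Sleep data will be processed as in Aim 1B".
- **Aim 2B.** Infant sleep is compared at 6 and 16 weeks with "mixed-effects models with Treatment, Time, and their interaction as fixed effects". No covariance structure is named.
- **Data collection.** Mothers wear the monitor for 7 days at each of two prenatal sessions, at 6 weeks ("Participants wear an activity monitor again for 7 full days") and at 16 weeks. The 12-week contact is by phone with no monitor, so there are two postpartum bursts. The infant sensor is worn for four days at 6 and at 16 weeks.

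**The concern.** A single intercept per woman says that she departs from her group's mean by the same amount at every session. In practice a whole week can be shifted by illness, work, or how the infant is sleeping at that age. Such a shift is constant over the burst and absent from the next one. AR(1) correlation decays from day to day, so it picks up only part of the shift, and the model then treats the days of a burst as carrying more independent information than they do.

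This matters for any contrast between sessions: the Time effect in Aim 1B, and Treatment x Time wherever daily data are fitted this way. The variance left out is the variance those contrasts depend on. The result would be intervals that are too narrow and too many significant interactions on sleep.

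**Working it through.** **The nearest stated figure.** The Power analysis gives a detectable d = 0.48 for Aim 1 (N = 214, 5% attrition, alpha 0.01). With 107 x 0.95 = 101.65 per arm, two-sided alpha and 80% power (sidedness, and power for Aim 1, are assumed):

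(2.576 + 0.842) x sqrt(2/101.65) = 0.479.

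The figure reproduces as a single-time-point comparison. It contains no day-level or session-level variance, so it cannot settle this point. The documents give no standard error or power for actigraphy.

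**Inputs**
- From the documents: two sessions; 7 days (mothers) or 4 days (infants) per session; alpha 0.01; 142 completers, so 71 per arm. The ratios below do not depend on the number per arm.
- Assumed: total day-level variance 1; woman (or infant) share 0.30; session share 0 to 0.30; day-to-day correlation rho 0 to 0.4; AR(1) restarting at each session.

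**Method**
1. True covariance: woman variance, plus woman-by-session variance, plus AR(1) days within session.
2. Planned covariance V: woman variance plus AR(1) within session, at the values that minimise log|V| + tr(V^-1 V0), where V0 is the true covariance. This is where maximum likelihood settles in large samples.
3. Ratio = model-based standard error of Treatment x Time / its true (sandwich) standard error.
4. True level of a nominal 0.01 test = 2 x Phi(-2.576 x ratio).

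**One case by hand** (mothers, session share 0.10, rho 0.2). The mean of the 7 x 7 AR(1) matrix is (7 + 2 x 1.4375)/49 = 0.2015. The variance of a session mean around the woman's own level is 0.10 + 0.60 x 0.2015 = 0.2209. The true standard error of the interaction is about sqrt(4 x 0.2209/71) = 0.112 (0.111 with optimal weighting). The planned model reports 0.093. The ratio is 0.83, and 2 x Phi(-2.576 x 0.832) = 0.032. The fitted AR(1) correlation rises from 0.20 to 0.28, so it absorbs part of the session variance but not all.

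**Ratio (true level of a nominal 0.01 test)**

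| Session share | Mothers, rho 0 | Mothers, rho 0.2 | Mothers, rho 0.4 | Infants, rho 0 | Infants, rho 0.2 | Infants, rho 0.4 |
|---|---|---|---|---|---|---|
| 0 | 1.00 (0.010) | 1.00 (0.010) | 1.00 (0.010) | 1.00 (0.010) | 1.00 (0.010) | 1.00 (0.010) |
| 0.05 | 0.86 (0.027) | 0.90 (0.020) | 0.93 (0.016) | 0.94 (0.016) | 0.96 (0.014) | 0.98 (0.012) |
| 0.10 | 0.77 (0.046) | 0.83 (0.032) | 0.89 (0.023) | 0.89 (0.022) | 0.93 (0.017) | 0.96 (0.014) |
| 0.20 | 0.68 (0.079) | 0.75 (0.053) | 0.82 (0.035) | 0.84 (0.031) | 0.88 (0.023) | 0.93 (0.017) |
| 0.30 | 0.64 (0.098) | 0.71 (0.067) | 0.79 (0.043) | 0.81 (0.037) | 0.86 (0.026) | 0.91 (0.019) |

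The Aim 1B Time contrast, also two bursts of 7 days, has the same ratios as the maternal columns. The Treatment effect averaged over sessions has ratio 1.00 throughout, with complete data.

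**Other readings of the covariance** (rho 0.2, session shares 0.05 to 0.30)
- AR(1) running on across the gap between sessions: mothers 0.86 to 0.61, infants 0.89 to 0.70. Here some bias remains at a session share of zero: reported against correct standard error is 0.0858 against 0.0888 for mothers and 0.1090 against 0.1147 for infants.
- Daily data with a random intercept and no AR(1): mothers 0.72 to 0.45, infants 0.78 to 0.56.

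**Simulation check** (1,500 runs; mothers, session share 0.10, rho 0.2). At nominal 0.05 the planned model rejects 10.5%, against 5.3% with a session intercept. At nominal 0.01 the figures are 2.7% and 1.7%. The simulation error at a true 1% is sqrt(0.01 x 0.99/1500) = 0.26 percentage points, so the 0.05 comparison is the firmer one.

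**The case against.** A reader might infer that the Treatment x Time tests on maternal and infant sleep are wrong as written. The documents do not support that, for these reasons.

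- **The model that is spelled out contains no Treatment term.** Within Aim 1B the exposed contrast is Time alone.
- **The carry-over to Aim 2 is partly inferred.** The sentence that refers back to Aim 1B is in the infant paragraph, whose models exclude the interaction, and it may concern data handling only. The maternal Aim 2A model names only subject intercepts and treats actigraphy alongside single-score questionnaires. That fits one value per session, which would be sound. Aim 2B names no covariance.
- **The session variance is not given.** At zero, with AR(1) restarting each session, there is no bias. The top of the range also needs independent days, although the plan itself assumes serial correlation; at rho 0.2 to 0.4 the highest levels are 0.067 for mothers and 0.026 for infants.
- **Part of the shift is modelled for infants.** Weaning, solid food, return to work and social support enter as time-varying covariates.
- **Primary status is not shown.** The Power analysis counts five primary outcomes without naming them, and Aim 2A lists five questionnaire or interview scales with actigraphy in addition.

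All of this stands, and it limits scope and size. It does not remove the point. The Aim 1B model is explicitly daily and has no term for the burst, and nothing says that Aim 2 uses session means. The time-varying covariates also show that the sponsor expects individuals to change between sessions.

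**Conclusion.** The point holds conditionally. The Aim 1B model understates the uncertainty of its Time effect if women vary between sessions beyond a constant intercept. Treatment x Time in Aims 2A and 2B shares the fault only if daily values are fitted in the same way.

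Under the assumptions listed with the inputs, the loss runs from nothing at a session share of zero to the figures at shares of 5-30%: maternal standard errors about 7-36% too small (true level 0.016-0.098 at nominal 0.01) and infant ones about 2-19% (0.012-0.037). It is larger if AR(1) is dropped for daily data or runs across the gap between sessions. These are sensitivity ranges, not estimates for this trial. The 0.01 threshold is itself an assumption for actigraphy.

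The fallback test of the averaged Treatment effect is unaffected in complete data. The separate inconsistency over infants, with no interaction in Aim 2A and one in Aim 2B, needs resolving in any case. This is a cheap improvement that should be made, with moderate confidence.

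**What to change.** 1. For each of Aims 1B, 2A and 2B, state whether the analysed value is daily or one mean per session.
2. For daily data, add a woman-by-session (for infants, infant-by-session) random intercept and nest AR(1) within session. Alternatively, analyse one mean per session. In the case worked by hand the two routes give standard errors of 0.111 and 0.112 for mothers, and both give 0.130 for infants.
3. Reconcile the infant paragraph of Aim 2A with Aim 2B on whether Treatment x Time is in the model.

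The cost is a few sentences and one variance parameter. Intervals for Treatment x Time may widen: in the same case the reported maternal standard error goes from 0.093 to 0.111 and the infant one from 0.121 to 0.130. If session variance proves negligible, the results barely change.

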**Power analysis** We adjusted for multiple comparisons (five primary outcomes across Aims 1 and 2) using Bonferroni correction, resulting in a significance threshold of 0.01. For Aim 1, with  $N = 214$  and an assumed 5% attrition, our mixed-effects model analysis is powered to detect a minimum effect size of  $d = 0.48$  (assuming within-subject correlation  $r = 0.2$ ). Prior research has shown larger effects (e.g.,  $d = 0.85$  for EPDS in mindfulness-based therapy), indicating our design has ample power. For Aim 2, assuming 33% attrition and five primary outcomes, power calculations show that  $N = 107$  per group is sufficient to detect interactions as small as  $d = 0.087$  with 80% power at a Bonferroni-adjusted  $\alpha = 0.01$ . Our preliminary data support this assumption. For Aim 3, based on tabulated recommendations 184 for sample sizes needed to test mediation effects, with  $N=142$  completers (assuming 33% attrition for assessments), we have more than 80% power to detect a significant mediation effect with moderate effect sizes ( $d=0.54$ ,

$r=0.26$  of both paths (i.e. the paths from treatment to the mediator(s) and the mediator(s) to outcomes). Since the full sample ( $N = 214$ ) will be used in mediation models, the actual power will exceed this estimate.

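### Aim 1B hypothesises better perceived sleep relative to objective sleep, but the only between-arm test it names is a difference in slope, which cannot detect a uniform gain in perception

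*Combined protocol and SAP*

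**What the plan says.** All of this is in the Statistical Analysis Plan.

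- **Hypothesis (Aim 1, part B):** PREPP will be associated with "Improved perception of sleep quality relative to objective changes in sleep duration", measured by self-report and actigraphy.
- **First stage (Analysis for Aim 1B):** actigraphic total sleep time and sleep efficiency are outcomes in mixed models. The listed fixed effects are time and day; Treatment is not among them.
- **Second stage (same paragraph):** "Subject-specific means of these measures will be used as predictors of their subjective" counterparts, in further mixed models "testing for treatment group differences in the association between objective and subjective sleep measures". The fixed effects of these models are not listed. The subjective counterparts carry the same labels as the actigraphic measures, so the self-report variable is not identified.
- **Nearest other test (Analysis for Aim 1A):** "For depressive symptom outcomes (HRSD, PHQ-9, HRSA, PSQI, EPDS), we will fit linear mixed-effects models with fixed effects for Treatment", together with Time and birth order. PSQI is one of the five scales, and actigraphy is not a covariate.
- **Power analysis:** a Bonferroni correction for five primary outcomes across Aims 1 and 2, "resulting in a significance threshold of 0.01", and a minimum detectable effect of d = 0.48 for Aim 1. The five outcomes are not listed there, and no figure is given for the association test.

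**The concern.** An improvement in perception relative to objective sleep is a directional statement about level. A group difference in association asks something else: whether perceived sleep rises more steeply with objective sleep in one arm than in the other. It has no stated direction, and neither sign of it means that perception improved.

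So the named test can be null when the hypothesis is true, and significant when it is false. Because the plan neither lists the model's terms nor says which coefficient answers Aim 1B, either the slope difference or the Treatment coefficient could be put forward once the data are seen.

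**Working it through.** **Inputs from the Power analysis:** N = 214 (107 per group), 5% attrition, alpha 0.01, d = 0.48, within-subject r = 0.2. **Assumptions not in the documents:** two-sided test; 80% power for Aim 1 (stated only for Aim 2); alpha 0.01 applies to Aim 1B; objective-subjective correlation ρ of 0.2 to 0.6; both measures scaled to SD 1; a shift of 0.48 SD, borrowed from the plan's own minimum detectable effect.

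**1. The plan's figure.** 214 × 0.95 = 203.3, or about 102 per arm. d = (z0.995 + z0.80) × √(2/n) = (2.576 + 0.842) × √(2/102) = 0.479. The stated 0.48 reproduces as a comparison of two means at one time point. It does not describe a slope comparison.

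**2. The named test under a uniform shift.** Write y = b0 + b1·T + b2·x + b3·T·x + e, with y subjective sleep, x objective sleep and T the arm. Then b3 is the PREPP slope minus the ETAU slope. Add a constant c to every PREPP woman's y. Her arm's covariance of x and y is unchanged, so its slope is unchanged; the residuals are unchanged too. Only b1 moves, by c. The estimate of b3, its standard error and its p-value stay the same, so the rejection rate is alpha for any c. Simulation (20,000 runs, 102 per arm) agrees: 0.9% to 1.1% at 0.48 SD for ρ = 0.2 to 0.6, and 1.0% at 0.85 SD (ρ = 0.4).

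**3. The adjusted Treatment coefficient under the same shift.** The residual SD is √(1 − ρ²), so the standardised effect is 0.48/√(1 − ρ²) and the noncentrality is that times √(102/2).

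| ρ | residual SD | standardised effect | noncentrality | power (noncentral t) |
|---|---|---|---|---|
| 0.2 | 0.980 | 0.490 | 3.50 | 81% |
| 0.4 | 0.917 | 0.524 | 3.74 | 87% |
| 0.6 | 0.800 | 0.600 | 4.28 | 95% |

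The normal approximation gives 82% to 96%. Using both prenatal assessments (r = 0.2, ρ = 0.4), simulation gives 99% for the Treatment term and 1.1% for the interaction.

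**4. A shift that varies with objective sleep.** With a mean shift of 0.48 SD and slopes differing by 0.24 SD per SD, the slope test rejects 19% to 32% of the time for ρ = 0.2 to 0.6 (about 27% at 0.5).

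**5. A slope difference with no mean gain.** With slopes differing by 0.48 and equal perceived sleep at average objective sleep, the slope test rejects about 80% to 94% of the time (90% at ρ = 0.5). The adjusted Treatment term stays near 1%.

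**6. What Aim 1A can see.** If PSQI carried the 0.48 SD shift, an unadjusted comparison at one time point has noncentrality 0.48 × √51 = 3.43 and about 79% power.

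**7. Subjective minus objective sleep as the outcome.** Its SD is √(2 − 2ρ). At ρ = 0.5 that is 1.00, and power is about 80% against 91% for the adjusted coefficient. At ρ = 0.2 it is 1.265, and power is 54% against 81%.

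**The case against.** **The hypothesis can be read another way.** Perception responding differently to objective sleep is a possible reading, and an association test would suit it. This stands as a caveat. But the hypothesis speaks of improvement, and a slope difference with no stated direction does not show improvement on either reading.

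**The model would normally contain a Treatment term, so this is only missing detail.** The plan never writes out the interaction, and a conventional model would include both terms. However, the plan does not list the Treatment term or name it as the test, whereas Aim 2A names its parameter of interest. Carrying out the test as named does not answer the stated hypothesis.

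**The 1% is true by construction.** Agreed: it is algebra, not evidence about this trial. A reader might infer that the test has no power against any gain in perception. That does not follow; step 4 shows partial power when the gain varies with objective sleep.

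**Aim 1A already tests perceived sleep.** Agreed, and Aim 2A repeats PSQI postpartum. A reader might infer that the trial would miss a gain in perceived sleep altogether. The documents do not support that: step 6 suggests PSQI would often show it. What is lost is the qualifier that Aim 1B adds, namely that the gain goes beyond any change in objective sleep.

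**Subject means.** A reader might also infer that these discard the change over time that the hypothesis mentions. The text does not say whether means are taken per monitoring week or across both, so this cannot be held against the plan.

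**Conclusion.** The concern holds in a limited form. Against a perception shift that is uniform across objective sleep, the only between-arm test named for Aim 1B has power equal to alpha. Against a shift that varies it has partial power, and it can be significant with no improvement. These conclusions rest on algebra and on reading the hypothesis as a difference in level, which is the most natural reading though not the only one.

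The figure of about 81% to 95% for the adjusted Treatment coefficient is conditional on the assumptions listed in the working; in particular, the documents give no objective-subjective correlation. The case for the change does not depend on where in that range the truth lies. The matter should be corrected, but it leaves the trial's other tests of perceived sleep intact.

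**What to change.** In the Analysis for Aim 1B:

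1. Name the subjective variable (diary or other self-report) and list the fixed effects of the association model: Treatment, centred objective sleep from the same monitoring epoch, and Time.
2. Make the Treatment coefficient the Aim 1B test. Report the 34-39 week contrast, because randomisation takes place at the 28-32 week session and the documents do not say whether that monitoring week falls before or after the first PREPP contact.
3. Keep Treatment × objective sleep as a secondary analysis.
4. Report the unadjusted arm differences in subjective and in objective sleep beside the adjusted one.
5. If wanted, add subjective minus objective sleep as a sensitivity analysis where the units match. It fixes the slope at 1, so it is not equivalent to the adjusted coefficient.

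The cost is SAP wording and a change of test within the same model. Activity-monitor and sleep-diary data are already collected at both prenatal sessions, so no new visits or participants are needed. The small downside is that objective sleep is measured after randomisation, so the adjusted contrast is not a purely randomised comparison; item 4 is there for that reason.
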